23 peginterferon-alpha 2a (PEGASYS®, Roche), 180 mcg per week administered by subcutaneous
24 injection for a total of 24 weeks. Patients will continue treatment with their previous nucleosi(t)ide
25 analogue regimen during the treatment and follow-up phases of this study.

26 Patients will be seen in the outpatient clinic at weeks 2, 4, 8, 12, and 24, during treatment phase, at
27 12 week intervals thereafter up to 48 weeks post-therapy

28 Compliance will be monitored by medication diaries and counting of the residual vials returned at
29 outpatient visits. The side effects will be monitored regularly at each visit during the treatment phase
30 of the study by symptom questionnaires. Peginterferon alfa-2a will be dose reduced or stopped per
31 the dose reduction and stopping rules for peginterferon alfa-2a. Peginterferon alfa-2a treatment can
32 be restarted if the adverse event resolves and the patient is willing to re-start the medication.

33

34 **On-treatment liver biopsy**

35

1 At day 0, all patients will be readmitted to the NIH Clinical Center to start therapy with peginterferon
2 alfa-2a and to undergo a repeat liver biopsy. Biopsy will be scheduled at 6 hours following the first
3 injection of peginterferon, for the purpose of assessing ISG response pattern following the initial
4 exposure to peginterferon. Liver tissue will also be subjected to routine histopathological grading
5 and staging as well as for immune cell, quantitative viral kinetic and cccDNA epigenetic studies as
6 previously described.

7
8 Since the hypothesis to be tested in this study is that response to treatment peginterferon (i.e. loss of
9 HBeAg and HBsAg or both) is mediated by changes in hepatocyte gene transcription profile, it is
10 necessary to obtain liver tissue at two time points-before and 6 hours after the first dose of
11 interferon. Performing two liver biopsies within 12 weeks or even as short as 24 hours has been
12 performed in other Liver Disease Branch studies and has not been associated with an increase in the
13 complication rate or lower patient acceptance.

16 **Monitoring**

17 Day 0

- 18
- 19
- 20 1) Brief clinical evaluation
- 21 2) Review patient's eligibility for study
- 22 3) Symptom questionnaire
- 23 4) Visual analogue scale
- 24 5) Fatigue questionnaire (Promise 7)
- 25 6) Chemistry 20 (sodium, chloride, potassium, bicarbonate, calcium, phosphate, magnesium,

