13 c) **Any clinical adverse event, laboratory abnormality, or intercurrent illness**, which in the
14 opinion of the investigator indicates that continued participation in the study is not in the
15 best interest of the subject. If any of the following laboratory or clinical criteria is obtained
16 for any subject, the result must be repeated/confirmed within 72 hours. If the results are
17 confirmed, the subject must discontinue treatment. Clinical criteria must have Principal
18 Investigator or Sub-Investigator assessment prior to permanent discontinuation.
- 19 – Evidence of confirmed hepatic decompensation (Child-Pugh Class B or C, Score > 6)
20 (discontinue all treatment);
 - 21 – Platelets < 25 x 10⁹ cells/L;
 - 22 – Hemoglobin <8.5 g/dL
 - 23 – Absolute neutrophil count < 250 mm³/ml
 - 24 – Severe neuropsychiatric signs and symptoms (including depression) for both new and
25 worsening events that are considered clinically significant by the investigator.
26
- 27 d) **Pregnancy** women of childbearing potential must contact the investigator or study staff
28 immediately if they suspect they might be pregnant (eg, missed or late menstrual period) at
29 any time during study participation. If subjects become pregnant the research staff will stop
30 peginterferon, but subjects may continue taking their antiviral oral agent at the discretion of
31 the study doctor. The investigator will discuss possible management options with the
32 subject. Subjects who do become pregnant will continue to be followed for the outcome of
33 the pregnancy. The NIH will not cover any aspects of obstetrical, child or related care.
34

- 1 e) **Loss of ability to freely provide consent** through imprisonment or involuntary
 2 incarceration for treatment of either a psychiatric or physical (eg, infectious disease) illness.

3

4

5 **Stopping NUCs therapy**

6

7 Treatment with NUCs will be stopped under the following conditions

- 8 a) HBeAg loss, with or without anti HBe seroconversion, in eAg positive patients, that is
 9 confirmed on 2 separate tests, at least 6 months apart.
 10 b) HBsAg loss, with or without anti HBs seroconversion, that is confirmed in 2 separate tests, at
 11 least 6 months apart.

12

13

14

15 **Peginterferon Dose Modifications**

16

17 Dose modification of peginterferon α -2a should be managed according to Table 2. This table is based
 18 on recommendations from the peginterferon α -2a package insert, and have been modified as

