 19 necessary for this study. As Tables 2 is a guideline, investigators may modify the dose based on
 20 clinical judgment.

21

22

23

Table 2: Peg-Interferon Alfa-2a Dose Modification Guidelines

Laboratory Value/Clinical Criteria:	Dose Modification:	Additional Instructions:
ANC:		
$\geq 0.75 \times 10^9$ cells/L	Maintain at 180 μ g	
$\geq 0.25 \times 10^9$ to $< 0.75 \times 10^9$ cells/L	Reduce to 135 μ g	
$< 0.25 \times 10^9$ cells/L	All study drugs should be interrupted until ANC values return to more than 1000/mm ³	Reinstitute at 90 μ g and monitor ANC
Platelets:		

$\geq 50 \times 10^9$ cells/L	Maintain at 180 μ g	
$\geq 25 \times 10^9$ to $< 50 \times 10^9$ cells/L	Reduce to 90 μ g	
$< 25 \times 10^9$ cells/L	Discontinue all study drugs if value is confirmed	Treatment should not be reinstated
ALT:		
ALT $> 10 \times$ ULN	Reduce to 135 μ g or interrupt all study drugs if repeated ALT results are $> 10 \times$ ULN	If ALT increases are progressive or there is evidence of hepatic decompensation therapy should be interrupted
New Ocular symptom(s):		
New decrease or loss of vision or other clinical significant ocular sign or symptom	Interrupt all study treatment	Complete eye examination must be performed.
New or Worsening Neuropsychiatric Signs or Symptoms (Including Depression):	Mild No change Evaluate weekly by visit or phone until symptoms improve.	Evaluate weekly (with visit at least every other week). Consider psychiatric consultation if no improvement. If improved and stable for 4 weeks, may resume normal dosing.
Moderate	Reduce dose to 135 μ g	
Severe	Discontinue all study drug treatment	Psychiatric therapy necessary. Treatment should not be reinstated.
Creatinine Clearance (CrCl):		
< 30 mL/min	Reduce to 135 μ g	
Hemodialysis	Reduce to 135 μ g	

1 Source: adapted from Pegasys® package insert.

2

3

STATISTICAL ANALYSIS

Power calculation

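### The peginterferon restart sentence has no exception for the two events after which Table 2 rules out reinstatement

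*Combined protocol and SAP*

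**What the plan says.** Three places in the combined protocol and SAP bear on this.

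- **Initiation of Treatment.** Dose reductions and stops follow the protocol's own rules for peginterferon. The next sentence says treatment can "be restarted if the adverse event resolves and the patient is willing to re-start the medication". The conditions are resolution and willingness; no type of event is carved out.
- **Table 2, Peginterferon Dose Modifications.** For platelets below 25 x10^9/L the action is "Discontinue all study drugs if value is confirmed", and the additional instruction is against reinstatement. For severe neuropsychiatric signs or symptoms the action is to discontinue, with the instruction "Psychiatric therapy necessary. Treatment should not be reinstated". No other row carries a bar on reinstatement.
- **Stopping peginterferon therapy, item c.** Five laboratory or clinical criteria must be repeated or confirmed within 72 hours. Both events above are on the list. The rule for results that are verified reads "confirmed, the subject must discontinue treatment. Clinical criteria must have Principal"; the sentence begun there goes on to require assessment by an investigator before discontinuation is made permanent.

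**The concern.** Read on its own, the restart sentence allows a patient to go back on peginterferon after an event that Table 2 treats as a final stop. The condition that the event has resolved does not protect the patients Table 2 has in mind. The CNS paragraph of the risk section says that the more severe psychiatric effects (paranoia, delusions, marked anxiety) clear one to two weeks after the drug is stopped. Such a patient could soon meet both restart conditions. The same section warns of life-threatening or fatal neuropsychiatric reactions in fewer than 1% of treated subjects, including people with no psychiatric history.

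What is at stake is patient safety. The interferon-stimulated-gene comparison uses a biopsy taken six hours after the first injection, before any restart could arise. The sample-size calculation (29 and 27 patients, raised to 30 per group for withdrawals) makes no assumption about restarting.

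**Working it through.** The main check compares texts; the plan has no figure of its own to reproduce.

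**1. The rules side by side**

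| Event | Restart sentence | Table 2 | Stopping rules, item c |
|---|---|---|---|
| Severe neuropsychiatric | Allowed if resolved and patient willing | Discontinue; no reinstatement | Mandatory stop; as a clinical criterion, assessed before permanent discontinuation |
| Platelets <25 x10^9/L, confirmed | Allowed if resolved and patient willing | Discontinue; no reinstatement | Mandatory stop |

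Two Table 2 rows bar reinstatement and the restart sentence contains no exception, so the texts conflict for exactly these two events. Table 2 and item c point the same way on stopping. For the neuropsychiatric event, both also indicate finality. For platelets, the explicit bar rests on the Table 2 row.

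**2. Can a patient meet both restart conditions with treatment still to come?**

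Assume 24 weekly doses at weeks 0 to 23, and a severe psychiatric event at week 8 that leads to a stop. With resolution in one to two weeks:

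- resolved at week 9: doses at weeks 9 to 23 remain, 23 − 9 + 1 = 15;
- resolved at week 10: doses at weeks 10 to 23 remain, 23 − 10 + 1 = 14.

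The conflict can therefore arise during the treatment period.

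**3. How many such events?**

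The CNS paragraph reports more severe psychiatric effects in 5% of the group's interferon-treated patients. With 60 patients, 60 × 0.05 = 3 expected events. This is an expected count, not a maximum, and it counts events rather than restarts. The plan does not equate these effects with the severe grade in Table 2. The figure is probably too high here, because the effects were seen largely in patients with existing psychiatric or neurological problems, and exclusion criterion 15 removes many with psychiatric problems.

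**4. How likely is the platelet case?**

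Assume an entry floor of 70 x10^9/L (the unit in exclusion criterion 13 is garbled, but the liver-biopsy risk paragraph uses 70,000/mm³). The risk section gives falls of 13% to 52%:

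- 70 × (1 − 0.13) = 60.9;
- 70 × (1 − 0.52) = 33.6;
- fall needed to reach 25: 1 − 25/70 = 64%.

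Even a patient entering at the floor would need a fall beyond the reported range, so this case is remote.

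**The case against.** The best defence is that the texts can be read together. The sentence just before the restart permission sends the reader to the dose-reduction and stopping rules. The permission itself is only that treatment can be restarted, not that it must be. It has proper work to do for events that Table 2 interrupts rather than ends: very low neutrophils, ALT above 10 times the upper limit, new ocular symptoms. A general permission followed by specific prohibitions is ordinary drafting, and most investigators would probably follow the specific row. To restart after severe paranoia, an investigator would have to disregard Table 2 and item c, in a study whose safety data are reviewed weekly.

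Most of this stands, and it is why the point is small. It does not remove the conflict. The pointer covers reducing and stopping; the restart sentence is separate and is not made subject to it. No text states precedence.

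A reader might infer something stronger: that the plan leaves it open whether these two stops are final. Two features invite that reading, and neither supports it.

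- Table 2 is described as a guideline: "necessary for this study. As Tables 2 is a guideline, investigators may modify the dose based on" clinical judgment. The latitude given is to modify the dose. It does not extend to reinstating treatment after an event for which reinstatement is barred, and the mandatory stop in item c is not described as a guideline.
- Item c also lists "Absolute neutrophil count < 250", whereas for the same neutrophil threshold Table 2 says "All study drugs should be interrupted until ANC values return to more than" 1000/mm³ and then reinstitutes at 90 µg. That is a real mismatch, but a separate one. It shows at most that the neutrophil stop is not final and says nothing about the other two events.

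**Conclusion.** The inconsistency is real but minor. The restart sentence, taken literally, permits what two Table 2 rows forbid. Table 2 and item c together make the intended rule clear, so the restart sentence is the one in error. This is a slip of wording with safety relevance, not a design choice.

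In practice it concerns a severe neuropsychiatric event in a few patients at most. It would be wrong to infer that about three patients would be re-exposed: the documents give no rate of wrongful restart and none can be derived from them. The conclusion about the text needs no assumption. The remarks on size rest on the risk section's 5% and 13–52% figures, the assumed platelet floor and the assumed dosing calendar. A correction is still worthwhile, because a safety rule should not depend on which section the investigator has open.

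**What to change.** Add one clause to the restart sentence in Initiation of Treatment: *except after severe neuropsychiatric events or confirmed platelets <25 x10^9/L, for which Table 2 rules out reinstatement*.

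Name the two events rather than excepting item c as a whole. A blanket exception would contradict the reinstitution at 90 µg after ANC <0.25 x10^9/L, which should stay unchanged. It would also sweep in "Hemoglobin <8.5 g/dL", for which Table 2 has no row. The neutrophil mismatch between item c and Table 2 should be settled as its own item. The same amendment could correct item a of the stopping rules, which sends the reader to Table 1 for guidelines that are in Table 2.

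The cost is one clause in an amendment, with no change to visits, data collection or analysis.
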